## 6. Patients and methods

### 6.1 Subject eligibility

Patient selection takes place on the basis of the inclusion and exclusion criteria

### 6.2 Inclusion criteria

- Legally competent male and female individuals aged from 35 to 85 years with a history of systemic sting reaction ( $\geq$  grade I according to the classification by Ring and Messmer, *Table 1*).
- Age  $\geq$ 35 and  $\leq$ 85 years

### 6.3 Exclusion criteria for phase 2 (no exclusion criteria for phase 1)

- Absolute contraindications for VIT
- Pretreatment with Omalizumab

## 6.4 Methods

### 6.4.1 Personal history

6.4.2 Personal history is recorded at Visit 1 if patients have met inclusion and exclusion criteria. Previous sting reactions, allergies, diseases and current medication will be recorded in the CRF.

Symptoms will be divided into subjective and objective symptoms. Subjective symptoms are: feeling of warmth, isolated pruritus, headache, general fatigue, anxiety, dysphagia, throat tightness, chest tightness, nausea, vertigo, perception of impending doom

Objective symptoms are: flush, urticarial, angioedema, dyspnea, hoarseness, drop in blood pressure, tachycardia, vomiting, abdominal cramping, bronchospasm, involuntary urination, involuntary defecation, loss of consciousness, cardiac arrest, apnoea

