### 5.2 Secondary objectives

- To evaluate whether subjects under antihypertensive treatment with beta-blockers and/or ACE-inhibitors have more severe sting reactions.
- To correlate the prevalence of cardiovascular diseases and/or hypertension with the risk for more severe systemic sting reactions and with more severe and more frequent side effects under VIT.
- To evaluate whether bee venom is associated with a higher frequency of side-effects.
- To evaluate whether high sIgE levels are correlated to a higher frequency of side-effects.
- To evaluate whether high tryptase levels are correlated to a higher frequency of side-effects.
- To evaluate whether quicker up-dosing protocols are correlated to a higher frequency of side-effects.
- To evaluate efficacy of VIT by sting challenges or field stings and look for differences between patients with and without antihypertensive treatment

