## 8. Schedule of study procedures

### ***Phase 1 (Screening, inclusion) – Visit 1. (week 0)***

The following procedures will be performed:

- Ask the subject to read and sign the Informed Consent
- Review of inclusion and exclusion criteria
- Collect medical and allergy history, recording of co-medication
- Collect demographics
- Perform skin testing and determination of IgE and serum tryptase (CAP)
- Record decision regarding venom immunotherapy (yes/no)

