### ***Phase 2 (up-dosing of VIT) – Visit 2. (0-4 weeks after reaching maintenance dose)***

- Re-collect medical history, recording of co-medication
- Record of up-dosing scheme and of the respective venom used for VIT
- Record pre-treatment during VIT
- Record of side-effects during VIT up-dosing

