***Phase 3 (maintenance phase) – Visit 3/3a (at least 12 months [+/- 2 months] after reaching maintenance dose)***

- Re-collect medical history, recording of co-medication
- Record of side-effects during VIT maintenance phase

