## **11. Statistical methods**

All patients who participate in this study belong to one of the following two groups for the analyses: the group without antihypertensive medication, and the group on antihypertensive medication (beta blockers and/or ACE inhibitors). The analyses will be based on the patients who completed buildup phase of immunotherapy.

Categorical variables will be described with percentages, and continuous variables will be expressed as means  $\pm$  standard deviation or median with interquartile range.

Statistical analysis will be performed using IBM SPSS Statistics 21. A 5% level of significance will be used throughout. In all analyses, an appropriate transformation may be used to obtain approximate normality.

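### Sting severity by drug group would be analysed on medication recorded after the sting, and Section 11 gives no dated rule for drug group when records differ

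*Combined protocol and SAP*

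**What the plan says.** All places are in the combined protocol and SAP.

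- **Objective.** Section 5.2 lists: "To evaluate whether subjects under antihypertensive treatment with beta-blockers and/or ACE-inhibitors have more severe sting reactions".
- **Visit 1 record.** Section 6.4.1: "Previous sting reactions, allergies, diseases and current medication will be recorded in the CRF". The Phase 1 list in Section 8 has: "Collect medical and allergy history, recording of co-medication". Eligibility (Section 6.2) requires a past systemic sting reaction, so both records postdate the index sting.
- **Later records.** Visit 2 falls 0-4 weeks after the maintenance dose is reached. It lists "Re-collect medical history, recording of co-medication" together with "Record of side-effects during VIT up-dosing". Co-medication is taken again at Visit 3/3a alongside "Record of side-effects during VIT maintenance phase". Table 2 (Section 13.2) also marks it at the optional Visit 3b/c for later field stings or challenges.
- **Group definition.** Section 11: "All patients who participate in this study belong to one of the following two groups for the analyses", namely "the group without antihypertensive medication, and the group on antihypertensive medication (beta blockers and/or ACE inhibitors". No visit, date or time window is attached.
- **Reasons to expect change.** Section 3.2.3 reports that guidelines favour replacing ACE inhibitors where feasible. Section 3.1.3 calls beta-blockers a relative contraindication in venom-allergic patients.

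**The concern.** A drug can affect the severity of a sting reaction only if the patient was taking it when stung. The listed records begin at Visit 1, after the sting. If some patients stopped or replaced a drug in between, they enter the severity comparison in the wrong group. If the change had nothing to do with severity, the odds ratio is mildly diluted. If patients with worse reactions were more or less likely to change, the estimate is biased in a direction that cannot be known in advance, and an association can appear where none exists.

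The second, softer part concerns the groups used for side effects of immunotherapy. A patient can have different drug status at Visits 1 and 2, and Section 11 does not say which counts. Visit 2 is completed after build-up side effects are known, so without a rule the choice of record can be made once outcomes have been seen.

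**Working it through.** **1. Is medication at the index sting recorded anywhere?** The co-medication entries are at Visits 1, 2, 3/3a and 3b/c. The first three describe medication at or after Visit 1, and 3b/c concerns later stings. The allergy-history item at Visit 1 does not mention medication. No listed item covers the index sting.

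**2. Size for sting severity.** The exposed share of 24% is the plan's figure (Section 11.3), applied here to status at the sting. The odds ratio of 2.2 is borrowed from the plan's side-effect assumption. The 20% severe among unexposed patients and all stopping rates are assumptions.

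Per 1,000 patients, severe risk in the exposed = (0.25 × 2.2)/(1 + 0.25 × 2.2) = 0.3548. The true table is 85.16 severe and 154.84 mild among 240 exposed, and 152 severe and 608 mild among 760 unexposed. Patients who stopped before Visit 1 move to the unexposed row.

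- Equal stopping, 10%: (76.65 × 623.48)/(139.35 × 160.52) = 2.14. At 20% it is 2.08 and at 30% it is 2.03. With a true odds ratio of 1, the result stays 1.00.
- 20% of severe and 10% of mild stop: (68.13 × 623.48)/(139.35 × 169.03) = 1.80. A true 1.00 reads (38.4 × 627.2)/(172.8 × 161.6) = 0.86.
- 10% of severe and 20% of mild stop: (76.65 × 638.97)/(123.87 × 160.52) = 2.46. A true 1.00 reads (43.2 × 646.4)/(153.6 × 156.8) = 1.16.

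**3. The plan's own primary figure.** Inputs from Section 11.3: 200 exposed at 12.3%, 631 unexposed at 6%, two-sided 5%. Power = Φ[(|p1 − p0| − 1.96·SE0)/SE1], with SE0 from the pooled proportion and SE1 from the separate ones. Pooled proportion = (24.6 + 37.86)/831 = 0.0752; SE0 = 0.0214; SE1 = 0.0251; power = 0.80. The odds ratio is (0.123/0.877)/(0.06/0.94) = 2.20, and 831/0.63 = 1,319. The plan's figures reproduce.

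**4. What a Visit 1 rule would do to the primary comparison.** This rests on three assumptions that the documents do not state: Visit 1 status is used, the 200 is a Visit 1 count, and risk falls fully to 6% on stopping. If a fraction f of exposed patients stop before the first injection, the apparent exposed risk is 0.123(1 − f) + 0.06f. Correct classification instead compares 200(1 − f) at 12.3% with 631 + 200f at 6%.

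| f (assumed) | Odds ratio, Visit 1 status | Power, Visit 1 status | Power, correct status |
|---|---|---|---|
| 10% | 2.07 | 73% | 78% |
| 20% | 1.94 | 65% | 75% |
| 30% | 1.82 | 56% | 71% |

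**The case against.** For the primary endpoint, the text points towards status during immunotherapy. Section 5.1 asks whether patients under these drugs have more side effects during it, Section 11.3 describes the exposed group in the same terms, and Visit 2 collects co-medication under the up-dosing heading. Maintenance medication is recorded too. On that reading the data needed are largely planned already, and the power losses in step 4 do not arise. If the 24% in Section 11.3 already describes status during immunotherapy, the 200 is net of stoppers and power with correct classification stays at 80%. Full return of risk to 6% is also the case of greatest dilution. This objection stands against any claim of a demonstrated power loss. It does not supply a rule: no section says which record decides, or what happens to a patient who changes.

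A reader might also infer that patients with differing records have no group at all. Section 11 does not support that, since it places every patient in one of two groups; what is missing is the rule that decides which.

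On sting severity, only one secondary objective is affected, stopping unrelated to severity does little harm, and the larger shifts need a link between stopping and severity that the documents do not report. The case report form is not shown and may already hold some of this. These points limit the size of the problem; the plan as written still has no listed item for the exposure this objective needs.

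**Conclusion.** The point holds as a cheap improvement. Followed as written, the sting-severity comparison uses medication recorded after the sting, in a setting where the protocol itself gives reasons why medication may have changed. On the assumed inputs, an odds ratio of 2.2 would read 2.14-2.03 under equal stopping, and 1.80 or 2.46 if stopping is related to severity. The frequency of changes and any link to severity are unknown.

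For the primary endpoint the finding is a missing dating rule, with a Visit 2 record made after build-up outcomes are known. A reader might infer from step 4 that the trial stands to lose 5 to 16 points of power. That follows only under all three assumptions listed there, and the documents lean away from the first. The sample size itself is not in question.

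**What to change.** 1. **Visit 1:** add two yes/no items, beta-blocker use and ACE-inhibitor use at the index sting. Name these in Section 11 as the exposure for sting severity.
2. **Visit 2:** record status for both classes at the first immunotherapy injection, and the date of any later change.
3. **Section 11:** state that first-injection status defines the group for the primary analysis, with Visit 1 status as a sensitivity analysis. State that patients are neither reclassified nor excluded because of a change made after a reaction, since that would let the outcome determine exposure.

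The cost is two items at Visit 1, two items and a change date at Visit 2, and a few lines of text; no extra visit is needed. The downside is that medication at the sting is partly recalled, so some error will remain. If the case report form already captures any of this, only the Section 11 text is needed for that part. No view is taken on whether any drug should be changed.

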#### 3.1.1 Background

Four main types of adrenergic receptors ( $\alpha_1$ ,  $\alpha_2$ ,  $\beta_1$ ,  $\beta_2$ ) can be roughly distinguished according to their affinity to norepinephrine and epinephrine. In brief, stimulation of  $\beta_1$  receptors induces a positive chronotropic and inotropic effect on the heart as well as a renin release of the kidney.  $\beta_2$  stimulation results in dilatation of blood vessels and bronchioles, and  $\alpha_2$  stimulation induces contraction of blood vessels and bronchioles . Basically,  $\beta$  blockade inhibits the effect of both endogenously released and therapeutically administered epinephrine on  $\beta$  receptors in case of anaphylaxis. Therefore epinephrine treatment can be ineffective or due to the block of  $\beta_1$  and  $\beta_2$  actions may facilitate unopposed  $\alpha$ -adrenergic effects like bronchoconstriction and bradycardia .

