### **11.1 Analysis of primary endpoint**

The primary endpoint for the study is the presence of objective side effects during immunotherapy which is defined as binary outcome: yes if any grade of objective side effect occurred, no otherwise.

The primary analysis will compare the proportion of objective side effects between the groups using a Mantel-Haensel estimate of the odds ratio stratified by center. A logistic regression model will be used to control for other possible confounders: age, gender, cardiovascular disease, hypertension, chronic bronchial disease or asthma, total IgE, venom-specific IgE, tryptase levels, mastocytosis, skin test reactivity, and study centers.

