### **11.3 Sample size**

It is assumed that 24% of the patients will be on beta blockers and/or ACE inhibitors. A  $\chi^2$  test with a two-sided 5% significance level has a 80% power to detect the difference between the group without antihypertensive medication with 6% side effects during VIT and the group on beta blockers and/or ACE inhibitors with 12.3% side effects during VIT (OR = 2.2) when the sample sizes are 631 and 200 (a total sample size of 831), respectively.

The drop-out rate includes study dropouts (30%) who do not start immunotherapy and study dropouts (10%) who do not end immunotherapy. This results in a drop-out rate of 37% and a required number of 1319 patients.

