#### 13.1.1 Table 1A

*Classification of systemic reactions modified according to J. Ring and Messmer*

Grade I	Generalised skin symptoms (e.g. flush, generalised urticaria, angioedema)
Grade II	Mild to moderate pulmonary, cardiovascular (tachycardia, hypotension, dizziness), and/or gastrointestinal symptoms (nausea)
Grade III	Anaphylactic shock, loss of consciousness, life-threatening spasm of smooth muscles (bronchi, uterus, etc.)
Grade IV	Cardiac and/or respiratory arrest

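### Tachycardia alone meets the primary endpoint, yet beta-blockers blunt it, so the endpoint depends on exposure and can dilute a beta-blocker effect by an unknown amount

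*Combined protocol and SAP*

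**What the plan says.** Section 11.1 defines the primary endpoint as binary: "yes if any grade of objective side effect occurred, no otherwise". One qualifying sign is enough. The only definition of an objective sign is the list in section 6.4.1 (Personal history), which includes "drop in blood pressure, tachycardia, vomiting, abdominal cramping". It sets no heart-rate threshold and requires no accompanying sign. Table 1A also names tachycardia, under grade II.

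Section 3.1.1 explains that stimulation of beta-1 "receptors induces a positive chronotropic and inotropic effect on the heart" and that beta "blockade inhibits the effect of both endogenously released and therapeutically administered epinephrine" on beta receptors in anaphylaxis. It also mentions bradycardia as a possible effect under blockade. Bradycardia is not on the objective list.

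Section 11 pools beta-blocker and ACE-inhibitor users into one exposed group. Section 11.1 says: "The primary analysis will compare the proportion of objective side effects between the groups", by a Mantel-Haenszel odds ratio stratified by center, followed by a logistic model for confounders. Sections 11 to 11.2 contain no scoring of the primary endpoint without tachycardia and no analysis of it by drug class.

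**The concern.** One qualifying component of the outcome is a sign that part of the exposure suppresses. If a reaction shows only a raised heart rate, an untreated patient scores yes and a beta-blocker user with the same reaction may score no. Adjusting for covariates cannot repair this, because the fault lies in how the outcome is recorded and not in an imbalance between the groups.

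For this component the direction is clear: it lowers the odds ratio for beta-blockers. That matters because section 4 promises a clear statement on risk, while section 3.1.3 describes a standing relative contraindication. A null result would carry weight, and as planned the reader could not tell how much of it came from the symptom list.

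**Working it through.** **Inputs from section 11.3.** Event rates are 6% (unexposed) and 12.3% (exposed), with 631 and 200 evaluable patients. The plan states that a chi-square "test with a two-sided 5% significance level has a 80% power to detect the difference".

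**Reproducing the plan.**
- Odds ratio: (0.123/0.877) / (0.06/0.94) = 2.197, stated as 2.2.
- Pooled rate: (631 × 0.06 + 200 × 0.123)/831 = 62.46/831 = 0.0752.
- Standard error of the difference: 0.02139 under the null (pooled) and 0.02507 under the alternative.
- Power: Φ[(0.063 − 1.96 × 0.02139)/0.02507] = Φ(0.84) = 79.96%.
- Enrolment: 1 − 0.70 × 0.90 = 0.37, and 831/0.63 = 1319.

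The sample size calculation is sound on its own terms.

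**Assumptions, because the documents give no figures.** Let t be the share of events whose only objective sign is tachycardia, b the share of exposed patients on a beta-blocker (taken as 50-60%), and m the fraction of those events that blockade hides. Also take 12.3% as the rate before masking.

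Recorded exposed rate = 12.3% × (1 − t × b × m).

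Example with t = 10%, b = 60%, m = 1:
- Planned effect: 0.123 × 0.94 = 0.1156, so the odds ratio is (0.1156/0.8844)/(0.06/0.94) = 2.05.
- No true effect: 0.06 × 0.94 = 0.0564, so the odds ratio is 0.94.

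Results with full masking (m = 1) and b = 50-60%, at 631 and 200:

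| t | Recorded odds ratio (planned 2.20) | Power | Recorded odds ratio if no true effect |
|---|---|---|---|
| 0% | 2.20 | 80% | 1.00 |
| 2% | 2.17 | 78.5-78.7% | 0.99 |
| 5% | 2.12-2.14 | 76.1-76.8% | 0.97 |
| 10% | 2.05-2.07 | 71.8-73.3% | 0.94-0.95 |
| 20% | 1.90-1.95 | 61.9-65.4% | 0.87-0.89 |

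With half masking (m = 0.5) the loss is about half as large. For example, power is 76.1-76.8% at t = 10% and 71.8-73.3% at t = 20%.

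**Scoring tachycardia-only patients as no event in both groups.** Both rates are multiplied by (1 − t).
- t = 10%: 5.4% against 11.07%, odds ratio 2.18, power 75.8%.
- t = 20%: 4.8% against 9.84%, odds ratio 2.16, power 71.0%.

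The odds ratio returns to about 2.2 at the price of fewer events. Power is above that of the masked endpoint under full masking (71.0% against 61.9-65.4% at t = 20%). Under half masking it is slightly below (71.0% against 71.8-73.3%). The gain is mainly in validity.

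**The case against.** A reader might infer that the primary comparison is biased, and by a large amount. The documents do not support that.

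- Only reactions whose sole objective sign is tachycardia are affected. A patient who also has flush, urticaria, dyspnea or a drop in blood pressure still scores yes. The documents give no frequency for isolated tachycardia, and if it is zero there is no bias.
- Only the beta-blocker part of the exposed group is affected. The protocol describes no heart-rate blocking for ACE inhibitors.
- The power losses treat 12.3% as a rate before masking. Section 11.3 gives it as the rate in patients on these drugs, without a source. If it is already the recorded rate, planned power is not reduced.
- The net direction across all the listed signs is not shown.
- Section 6.4.1 mentions the CRF for the Visit 1 history. For up-dosing, section 8 and Table 2 say only that side effects are recorded, so re-scoring may need more than one extra run.

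All of this stands, and it limits the claim to a possible bias of unknown size. It does not remove the mechanism, which follows from the protocol's own text, or the absence of any planned check. Not knowing the tachycardia-only share is itself a reason to fix the check in advance: if such events are rare the two scorings will agree, and an exclusion chosen after seeing the data would look selective.

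**Conclusion.** The point holds in conditional form. As written, the primary endpoint depends on exposure through tachycardia. It can dilute a beta-blocker effect, or make beta-blockers look protective if there is no true effect, and nothing planned would reveal this.

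Under the stated assumptions, the effect runs from none (no tachycardia-only events), through about 1 point of power at a 2% share, to an odds ratio of 1.90-1.95 and power of 62-65% at a 20% share with full masking. None of the three driving quantities is in the documents, so no single value in that range should be read as an estimate.

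Two further inferences should be avoided. The sample size is not in error: it reproduces. And agreement between two non-significant results, with and without tachycardia, would not show absence of harm. The two analyses share most of their events, the plan sets no margin, and the study is powered to detect a difference.

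**What to change.** Keep the stated endpoint and add one paragraph to section 11.1:

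- A pre-specified sensitivity analysis scores a patient whose only objective sign was tachycardia as no event, in both groups. It uses the same center-stratified Mantel-Haenszel odds ratio with its 95% confidence interval.
- Report it overall and, descriptively, for beta-blocker users (alone or combined) and ACE-inhibitor-only users.
- Interpret the primary odds ratio alongside this version through the confidence intervals. Do not use agreement of two non-significant results as evidence of no increase.

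Confirm that the Visit 2 side-effect record (section 8, Phase 2) captures each sign individually.

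**Cost.** If signs are recorded individually, the cost is a paragraph and one further analysis. If not, the side-effect form must change. The second version has fewer events (power about 76% at a 10% share and 71% at 20%). The drug-class breakdown will be imprecise: with 100-120 beta-blocker users (50-60% of 200) against 631 unexposed patients, power at the planned rates is about 61-66% even before any events are removed.

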### 6.4.3 Laboratory tests

Total and specific IgE (bee and vespид venom, rApi m 1, rVes v 1, rVes v 5) as well as serum tryptase will be determined.

Measurements will be performed as part of clinical routine procedures by ImmunoCAP® (Thermo Fisher Scientific, Waltham, MA, USA), according to the manufacturer's instructions.

### 6.4.4 Skin testing (Intradermal skin test and/or prick testing)

Skin testing is performed routinely within the standard diagnostic procedure of each center.

### 6.4.5 Venom immunotherapy (VIT)

There is no standard buildup phase; centers use their own standard protocols. Typically, conventional (outpatient), Cluster/Ultrarush- (partial inpatient) and Rush-protocols (inpatient) will be performed. The respective venom that is used for VIT will be recorded (bee or wasp venom, trade name, company). Injections will be administered subcutaneously in the dorsal part of the upper arm, one hand's breadth above the elbow, or in the volar part of the thigh. All interventions will be performed according to the in-house protocols of participating centers.

